9.7.1.5. Subgroup analyses

If the sample size allows for informative analyses, subgroups as defined in Section 9.3.4, will be analysed.

9.7.1.6. Adjustment for baseline imbalances

Propensity score methods will be used to estimate the adjusted risks, cumulative incidences, effect estimates and their corresponding 95% CIs to account for potential baseline confounding. Specifically, the propensity score (ie, the probability of receiving bivalent BA.1 or bivalent BA.4-5 vaccine conditional on baseline covariates listed in Section 9.3.3) will be used to construct inverse probability weights.^{40,41} More details, including the variable selection and construction of weights, will be provided in the SAP. The incidence of COVID-19-related outcomes in the first few days after baseline will be evaluated as a negative control outcome for baseline exchangeability.

Individuals would need to be censored at the time of a documented SARS-CoV-2 infection or COVID-19 diagnosis in order to estimate the direct effect only. The likely underreporting of SARS-CoV-2 infections and COVID-19 during the time when bivalent vaccination is available will mean that some of the estimated direct effects could be mediated through the prevention of SARS-CoV-2 infection or COVID-19 by the vaccination. It is expected that this will be important limitations to evaluating the direct effect. Therefore, the main analysis of this study will evaluate the total effect. In addition, sensitivity analyses (Section 9.7.1.11) will be carried out to estimate the direct effect. An additional censoring criterium, i.e., a documented SARS-CoV-2 infection or COVID-19, will be implemented to estimate the direct effect. The assumption behind this is that uncensored individuals will have a similar risk for the AESI as that of the censored individuals if they had not been infected, which is conditional on the matched covariates and other variables that will be adjusted for.

9.7.1.8. Censoring

Censoring to analyse individuals with complete follow-up and complete adherence to the vaccination strategies will be done to estimate the total effect of bivalent BA.1 or BA.4-5 vaccination on the risk for the AESIs.

The following censoring will be applied to estimate the total effect under complete follow-up and complete adherence to the vaccination strategies, as well as the corresponding assumptions for validity:

- **Censoring after loss to follow-up** (i.e., disenrollment from the data source). This censoring will be implemented to estimate the effect under complete follow-up. The assumption behind this is that individuals who do not disenroll from the data source have a similar risk of the AESI as the individuals who do disenroll from the data source if they had remained in follow-up, conditional on the matched covariates and other variables that were adjusted for.
- **Censoring due to unexposed individual receiving COVID-19 vaccination.** Censoring of the matched pair when the individual in the unexposed cohort receives a COVID-19 vaccine or when the individual in the exposed cohort receives a non-Pfizer vaccine will occur. This censoring will be implemented to estimate the effect under complete adherence to the vaccination strategies. The assumption behind this is that the risk of the AESI for individuals that did not deviate from the vaccination strategy would be similar to that of the individuals who deviated from the vaccination strategy, had they not deviated, conditional on adjustment of the matched variables and other variables.

9.7.1.9. Meta-analysis

A combined effect will be estimated using estimates from each data source and appropriate random-effects meta-analytical methods. The heterogeneity across data sources will be analysed, and forest plots will be produced containing the individual risk estimates plus the overall risk estimate.

9.7.1.10. Missing data handling

Several approaches for handling missing data will be considered (eg, inverse probability weighting of the complete case population, complete case analysis), based on the amount of missing data and the most reasonable assumption on the pattern of how the data are missing. Additional details on when and which method will be used will be described in the SAP.

9.7.1.11. Sensitivity analysis

One sensitivity analysis will estimate the direct effect of vaccination on the AESIs by repeating the main analyses and additionally censoring in the event of a documented SARS-CoV-2 infection. Another sensitivity analysis will exclude individuals who have had contact with the health care system in the 7 days before time zero. Contact with the health care system serves as an indicator of a health event not related to subsequent vaccination that could reduce the probability of receiving the vaccine.²²

If the homogeneity of the data allows, additional sensitivity analyses will be done to estimate the combined pooled effect across data sources.

9.7.2. Self-controlled risk interval design

9.7.2.1. Descriptive statistics

The distributions of individuals' characteristics at the time of vaccination with bivalent BA.1 or bivalent BA.4-5 will be calculated to characterise the study sample. Means, standard deviations, medians, and other quartiles will be estimated for continuous variables. Counts and proportions will be estimated for categorical variables. The missingness of variables will also be described.

9.7.2.2. Measures of association

Conditional Poisson regression will be used to estimate incidence rate ratios and their corresponding 95% CIs. AESI for which the SCRI design will be a secondary approach for AESIs, with their risk windows, are specified in [Table 1](#). The control period that will be the same length will follow the risk interval; more details will be provided in the SAP.

The SCRI inherently adjusts for both measured and unmeasured time constant factors such as sex and chronic health conditions with onset before the start of follow-up. Time-varying confounders may be included as covariates in regression models.

Analyses will be conducted in subgroups defined by demographic and clinical characteristics, dose number, and other covariates of interest when feasible.

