9.1.2. Self-controlled risk interval design

The SCRI design will be used as a secondary analysis to compare the occurrence of specific AESIs for which the design is recommended.²⁶ Occurrence of an AESI in a specified risk interval following a dose of bivalent BA.1 or bivalent BA.4-5 will be compared with the occurrence of the same AESI in a later interval (control interval), in the same individual. AESIs that are appropriate for this study design are those that are:

[figure not shown]
- rare, with a transient risk after exposure;
- have a constant event rate within the observation periods;
- have an occurrence that does not alter the duration of the observation window.²⁷

The SCRI design will be used to compare the risk of each AESI during a prespecified period following vaccine administration during which there is a hypothesised increased risk of the outcome ('risk period') with a self-matched control period, used to assess the baseline risk of the outcome.

The risk periods proposed for each AESI and the AESIs that will be analysed using the SCRI design are summarised in [Table 1](#).

A prespecified post-vaccination control period will be used for each outcome. The use of a control period after the risk period (rather than the use of a control period before the risk period) avoids bias from outcomes affecting the probability of exposure (eg, the outcome could be a contraindication for vaccination or could delay vaccination) (Figure 1).

Figure 1. Self-controlled risk interval design

T = time, in days.

Note: Example with a risk period of 42 days and a control period of 42 days.

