9.2.1.2. Self-controlled risk interval design

Individuals must meet all the following criteria to be eligible for inclusion in the SCRI design:

- have received a dose of Pfizer-BioNTech bivalent BA.1 or bivalent BA.4-5 vaccine;
- have not received any COVID-19 vaccine in the three months prior to the dose of bivalent BA.1 or bivalent BA.4-5;

PFIZER CONFIDENTIAL

CT24-WI-GL02-RF02 4.0 Non-Interventional Study Protocol Template For Secondary Data Collection Study

01-Jun-2022

Page 20 of 64

- have experienced the specific AESI during the risk or control interval;
- have full accrual of data used to define the event in both the risk and control interval combined, taking into account the data lag and timing of data extraction;
- have a minimum of 12 months continuous enrollment in the data source at time zero.

[figure not shown]

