Respiratory system	Acute respiratory distress syndrome	365	Cohort
Reproductive system	Secondary amenorrhea	183	Cohort
	Hypermenorrhea	183	Cohort
Skin and mucous membrane, bone and joints	Erythema multiforme	42	Cohort
	Chilblain-like lesions	42	Cohort
Other	Anosmia, ageusia	42	Cohort
	Anaphylaxis ^a	1 ³¹	Cohort/SCRI
	Multisystem inflammatory syndrome	42	Cohort
	Death (any causes)	365	Cohort
	Subacute thyroiditis	365	Cohort
	Sudden death	365	Cohort
Pregnancy outcome, maternal	Gestational diabetes	Any time pregnancy	Sub-cohort
	Preeclampsia	After 20 weeks gestation	Sub-cohort
	Maternal death	Any time pregnancy	Sub-cohort
Pregnancy outcome, neonates. Define design taking trimester into account	Foetal growth restriction	Any time pregnancy	Sub-cohort
	Spontaneous abortions	At spontaneous abortion	Sub-cohort
	Stillbirth	At birth	Sub-cohort
	Preterm birth	At preterm birth	Sub-cohort
	Major congenital anomalies ^a	1 year after birth	Sub-cohort
	Microcephaly	At birth	Sub-cohort
	Neonatal death	At birth	Sub-cohort
Termination of pregnancy for foetal anomaly	At termination	Sub-cohort	

090177e19fa902a7Approved\Approved On: 12-Jan-2024 21:20 (GMT)

Table 1. Safety outcomes: adverse events of special interest (AESIs) with estimated risk intervals and preferred study design

Body system / classification	Adverse event of special interest	Estimated risk interval (days)*	Preferred study design*
	Small size for gestational age	Any time pregnancy	Sub-cohort
Any	Severe COVID-19 ^b	Any	Cohort

SCRI = self-controlled risk interval

* Time zero corresponds to the day of vaccination (i.e., a 42-day risk interval means that individuals are followed from the day of vaccination to day 41). Risk interval based on the ACCESS project results and other publications.

a For these AESI clinical validation will occur.

b Severe COVID-19 defined as either COVID-19 hospitalisation or death

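### The equal-length SCRI control rule, with no stated gap, can place myocarditis and pericarditis control time inside the plan's own longer risk windows, and it leaves anaphylaxis with a one-day control

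*Protocol*

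**What the plan says.** Section 9.1.2 makes the SCRI a secondary analysis. Events in a risk interval after vaccination "will be compared with the occurrence of the same AESI in a later interval (control interval), in the same individual". The purpose of the control period is stated: it is "used to assess the baseline risk of the outcome". The same section adds: "A prespecified post-vaccination control period will be used for each outcome".

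Section 9.7.2.2 fixes length and order: "The control period that will be the same length will follow the risk interval". The same sentence leaves further details to the SAP. Neither section mentions a gap between the risk and control periods.

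Table 1 (Section 9.3.2) gives myocarditis, pericarditis and the two combined three risk intervals each: 7, 14 and 21 days. Anaphylaxis has 1 day. All four are marked for both cohort and SCRI analysis. The table's footnote counts from the day of vaccination as day 0: "a 42-day risk interval means that individuals are followed from the day of vaccination to day 41".

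**The concern.** A control period measures baseline risk only if it lies outside the time in which the vaccine may act. By listing three nested windows for the same event, the plan treats days 7-20 as possible risk time. An equal-length control placed directly after the shorter windows falls on those same days, so they count as risk time in one analysis and as baseline in another.

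Section 9.9 offers the SCRI as the answer to residual confounding in the cohort. A check that can return an IRR of 1 when the effect is real could reassure wrongly, on events that the plan also selects for clinical validation. The three IRRs for one event would also rest on different baselines and would be hard to compare.

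Anaphylaxis raises a separate issue. Equal length leaves a single control day wherever it is placed, so the denominator of the IRR may be nearly empty.

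**Working it through.** **Day counting.** An L-day risk interval is days 0 to L-1. For L = 42 this ends on day 41, as the Table 1 footnote states. An equal-length control starting directly afterwards is days L to 2L-1.

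**Overlap for myocarditis, pericarditis and the composite**

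| Analysis | Risk days | Control days | Control days inside a longer listed window |
|---|---|---|---|
| 7-day | 0-6 | 7-13 | 7 of 7 (inside both the 14- and 21-day windows) |
| 14-day | 0-13 | 14-27 | 7 of 14 (days 14-20, inside the 21-day window) |
| 21-day | 0-20 | 21-41 | 0 of 21 |

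Every other SCRI outcome in Table 1 has a single risk interval, so this overlap cannot arise there.

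**Expected IRR.** Let the true rate be R times baseline on days 0 to T-1 and baseline afterwards. The expected IRR is the mean daily rate in the risk window divided by that in the control window. The documents give no SCRI effect size. R = 2, 5 and 10 are borrowed from the risk ratio scenarios in Table 3.

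- T = 21, 7-day analysis: 7R / 7R = 1.0 for every R.
- T = 21, 14-day analysis: 14R / (7R + 7) = 2R / (R + 1), which gives 4/3 = 1.33, 10/6 = 1.67 and 20/11 = 1.82.
- T = 21, 21-day analysis: 21R / 21 = R, so 2, 5 and 10. No bias.
- T = 14: the 7-day analysis again gives 1.0; the 14-day analysis gives R.
- T = 7: the 7-day analysis gives R. The 14-day analysis gives (R + 1)/2 = 1.5, 3.0 and 5.5, but a control from day 21 gives the same values. That dilution comes from the length of the risk window, not from the control.

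**With control time from day 21.** The overlap is zero in all three analyses. With T = 21, each returns R (2, 5, 10).

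**Anaphylaxis.** Risk is day 0. The control is one day: day 1 on the contiguous reading. Expected control events = vaccinees x rate / 365.25 x control days. The documents give no background rate, so 10 per 100,000 person-years is assumed (range 1 to 50), with 1,000,000 vaccinees, the largest group size in Table 3.

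- One day: 1,000,000 x 10/100,000 / 365.25 = 0.27 (0.03 to 1.4).
- 42 days: 42 x 0.274 = 11.5 (1.15 to 57.5).
- Chance of no control event in one day: exp(-0.274) = about 76% (97% at rate 1, 25% at rate 50).

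A data source with no control events yields no finite IRR to carry into the random-effects pooling of Section 9.7.2.3.

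**The case against.** The strongest reply is that the position of the control period is not fully fixed. The text says that the control comes after the risk interval, not that it starts at once. Figure 1 is not reproduced in the text at hand and might show a gap. Details are deferred to the SAP, and Section 9.7 lets the SAP modify the plan. The sentence in Section 9.1.2 on a control period for each outcome can even be read as one common window per event. This stands in part: a gap set in the SAP would remove the overlap. But nothing in the protocol requires one. A single common window could match only one of the lengths 7, 14 and 21, so it would break the equal-length rule. And no gap changes the one-day anaphylaxis control.

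It is also fair that the analysis is secondary, and that Section 9.9 already admits that uncertain risk periods lead to underestimation. That admission describes the problem without limiting it.

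Three stronger readings are tempting, and the documents do not support them.

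- **That the rule biases the myocarditis and pericarditis IRRs as such.** It does so only if the excess outlasts the window analysed, and never through overlap in the 21-day analysis.
- **That the anaphylaxis IRR is biased toward no effect.** Day 1 lies in no listed anaphylaxis window. Such bias needs reactions that occur or are dated a day late; the documents give no share for this, and anaphylaxis is marked for clinical validation.
- **That later COVID-19 doses contaminate the control time.** SCRI eligibility does look only backwards ("have not received any COVID-19 vaccine in the three months prior to the dose of bivalent BA.1 or bivalent BA.4-5"). But Section 7 describes boosters as given at least three months after the last monovalent dose, while the longest contiguous SCRI observation is 84 days (2 x 42). The question is mainly confined to BA.4-5 primary series, whose size is not given, and ending observation at a next dose is ordinary SAP content.

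**Conclusion.** The concern holds in a limited form. On the plain contiguous reading, the stated rule puts all of the 7-day control time and half of the 14-day control time inside risk windows that the same plan lists for the same events. If a constant excess lasts 21 days, true IRRs of 2, 5 and 10 appear as 1.0 in the 7-day analysis and as 1.33, 1.67 and 1.82 in the 14-day analysis. These sizes rest on three assumptions: no gap, a constant excess, and effect sizes borrowed from Table 3. There is no bias when the excess ends within the window analysed.

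For anaphylaxis the finding is imprecision: about 0.27 expected control events per million vaccinees at the assumed rate. This follows from equal length alone and does not depend on the contiguous reading.

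The matched cohort estimates, which address the primary objective, are not touched. What changes is how much a secondary analysis meant to address residual confounding can show.

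**What to change.** In Section 9.7.2.2, replace the same-length rule with one prespecified control window per AESI that starts after the longest Table 1 risk interval for that AESI. For myocarditis, pericarditis and the composite, this means day 21 or later, with the same window for the 7-, 14- and 21-day analyses. Allow its length to differ from that of the risk window, and include log(length) as an offset in the conditional Poisson model. For anaphylaxis, use a control window of several weeks. Carry the same wording into the SAP before any SCRI result is seen, so that the windows remain prespecified as Section 9.1.2 promises.

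The cost is one paragraph and one programming parameter. The downside is small: control time lies somewhat further from vaccination, so adjustment for time-varying factors, which Section 9.7.2.2 already allows, matters slightly more.

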9.7.2.3. Meta-analysis

As in the cohort design, a combined effect will be estimated using estimates from each data source using appropriate random-effects meta-analytic methods. The heterogeneity across data sources will be analysed, and forest plots will be produced to display the individual and pooled estimates.

9.8. Quality control

Data transformation into the CDM will be conducted by each subcontracted research partner in its associated data source, using the processes described below. Standard operating procedures or internal process guidance at each research centre will be used to guide the conduct of the study. These procedures include:

- rules for secure and confidential data storage, backup, and recovery;
- methods to maintain and archive project documents;
- QC procedures for programming;
- standards for writing statistical analysis plans; and
- requirements for scientific review by senior staff.

9.8.1. University Medical Center Utrecht and RTI Health Solutions

At UMCU, the scientific coordinating centre responsible for central data management and analysis, all documents will undergo QC review and senior scientific review. Data management and statistical analysis will follow standard operating procedures. All statistical analysis programs will be double-coded.

At RTI Health Solutions (RTI-HS), the project coordinating centre and scientific coleader centre, all key study documents will undergo QC review, senior scientific review, and editorial review. Senior reviewers with expertise in the appropriate subject matter areas will provide advice on the design of research study approaches and the conduct of the study and will review results, reports, and other key study documents.

Rigorous QC will be performed for all deliverables.

9.8.2. Pedianet (IT)

Pedianet data processing will include QC steps that will verify the correspondence between diagnostic codes and their open-text descriptor through manual validation of clinical histories, in addition to standardised procedures in Structured Query Language (SQL) and Microsoft Access to extract data from the database. Quality control checks of individual general data will be conducted through the detection of outlier values and validation rules; grouping of diseases; and regular monitoring of aggregate clinical and drug data. All

transformations in the data will be logged in R scripts. To ensure code reliability, double programming in R and Stata or Python will be in place for all scripts.

9.8.3. PHARMO (NL)

PHARMO adheres to high standards throughout the research process based on robust methodologies, transparency, and scientific independence. PHARMO conducts studies in compliance with the ENCePP *Guide on Methodological Standards in Pharmacoepidemiology*⁴⁵ and the *ENCEPP Code of Conduct*¹⁴. PHARMO is ISO 9001:2015 certified. Standard operating procedures, work instructions, and checklists will be used to guide the conduct of the study. These procedures and documents include internal quality audits, rules for secure and confidential data storage, methods to maintain and archive project documents, rules and procedures for execution and QC of SAS programming, standards for writing protocols and reports, and requirements for senior scientific review of key study documents.

9.8.4. NHR (NO)

The University of Oslo will have centralised information security policies in place to ensure the confidentiality, integrity and availability of the organisation's systems and data. All data will be stored and analysed within the "Tjeneste for Sensitive Data" (TSD) platform, a service for sensitive data management at the University of Oslo.^{46,47} Only authorised researchers will have access to manipulate the data within the TSD, via a two-step authentication process. The study will be conducted in compliance with the *Guidelines for Good Pharmacoepidemiology Practices (GPP)*⁴⁸ and the *ENCEPP Code of Conduct*.¹⁴ Data quality is a high priority at the Norwegian Health Registries; updated data are released regularly for research purposes after centralised quality control. The University of Oslo will use their rules for secure and confidential data storage and analysis, as well as their rules for data cleaning, linkage, and programming.

9.8.5. EpiChron (ES)

The EpiChron cohort will be built from the BIGAN platform which integrates a technical infrastructure and a data lake, collecting individual data from the regional health service information systems. The BIGAN platform includes several mechanisms to control and improve the quality of data, mainly in the ETL processes for capture and persistence in the data lake. These mechanisms include validation rules (for example, for dates and time intervals) and cross-checks with master tables, requiring that certain coded data exist in a standardised dictionary. Analyses of the distribution of variables will also be carried out periodically, to detect 'outliers' that identify errors in the data capture or transformation processes. Generally, records that do not pass the quality assurance procedures are kept in a 'holding' area for review and decision to discard or reprocess. The resulting databases will be pseudonymised to encrypt individual-level identification codes, protecting individuals' privacy and complying with data protection laws. They will be stored on a central computer server, with access restricted to the members of the research group, via a two-step authentication process. The research group will comprise a multidisciplinary qualified team

including public health specialists, epidemiologists, clinicians, pharmacists, statisticians, and data managers, who are all trained in data management and data protection.

